Finally, to specify possible mechanisms of action to promote a behavior, such techniques and functions must be connected to influences on behavior following this model. The proposed mechanisms of action to facilitate adherence behavior in WelTel were: a) the delivery of an external trigger (SMS reminder to complete a behavior) and social support, to influence opportunities and automatic motivation through restructuring and environmental clearance; b) delivery of health-related information and social support to influence ability, opportunity, and motivation through education, persuasion, and training. We believe that retention in HIV care will be similarly influenced in our intervention.

General description:

This intervention will be designed for MSM who are HIV positive. We will recruit subjects 18 years of age or older. The intervention will begin one day after enrollment. The two-way SMS intervention will have four components: 1) an automated weekly SMS sent to ask how they are doing (basic follow-up); 2) phone calls from a health provider to participants who respond that they have a problem, or that they need support or some information that cannot be resolved by text message; 3) SMS reminder 1 week before an appointment for HIV care.

Design:

Randomized controlled trial.

Main result:

The primary outcome will be retention in HIV care for up to 1 year after enrollment. Participants will be classified as retained in care if they attend three HIV care appointments that are separated by 90 days or more within a one-year period (at the study HIV center) (64). Otherwise, they will be classified as not retained. The delivery of the intervention will last 6 months and the follow-up period to verify retention will last up to 12 months.

Main exposure:

Text message (SMS) based intervention delivered through the WelTel system by trained health providers.

Procedures:

- 1. **Recruitment and eligibility criteria**. We will identify and recruit 208 HIV+ MSM in the Cayetano Heredia Hospital HIV service for a period of up to 12 months. Eligible participants will be 1) men who have sex with men; 2) 18 years or older; 3) has been diagnosed HIV positive; 4) own a cell phone that can send and receive SMS; 5) resides in Lima; and 6) not be enrolled in another study that uses text messaging.

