- 2. Enrollment and randomization: During enrollment, the recruiter will be blinded to assignment to the intervention group. The recruiter will obtain informed consent and instruct the participant on how he should interact if he starts receiving text messages (see appendix 1). Participants will be randomly assigned after providing their cell phone number and brief general information (first name, date of diagnosis, email). They will be assigned a study ID and randomly divided into intervention or control arm (1:1 ratio) using computer generated random numbers. Arm assignments will be in sequentially numbered sealed envelopes. Healthcare providers trained to administer the intervention will be informed by the research team when a new participant is enrolled in the intervention arm. Due to the nature of the study, healthcare providers and participants will not be blinded to group assignment. The participants assigned to the intervention arm will have their telephone numbers registered on the platform.
- 3. Intervention. We will use the WelTel platform. For 6 months, every Monday the system will send automatic SMS with the question "How are you?" or similar questions (How are you?; How are you doing?). Participants will be instructed to respond if they are okay ("All OK") or if they have a problem ("I want support"; "I'm not okay"). The provider will send a return SMS to participants who have a problem or query; or they will call those who need it. The WelTel program has a customizable dictionary that identifies the words (or phrases) that the administrator indicates; thus, the answers of the participants are automatically ordered to indicate who needs follow-up through a reply SMS or call. One week before each appointment for HIV care, health providers will send an SMS reminder (Table 1).

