 Data sources for the main result. The main outcome to be measured will be retention in HIV care during the first year after enrollment. Retention in care will be considered if they attend 3 HIV care appointments that are at least 90 days apart within a one-year period (64). We will verify retention in HIV care with: study registration (enrollment) sheets, physical medical records from the HIV service, reception appointment notebooks, and with a final follow-up survey.

Health providers will enter the data from the enrollment registration sheets into a database that will be stored in a password-protected computer file. The data from the final follow-up online survey completed by the participants will be exported to the physical database and will be periodically deleted from the online survey system server. All data resulting from the interaction between providers and participants will be stored on the WelTel platform that has high security standards: encrypted, password protected and HIPAA compliant (*The Health Insurance Portability and Accountability Act*).

Statistic analysis. for the main outcome, we will compare the proportion of MSM who
were retained in care in both groups, as a cumulative incidence rate. If any variable of
interest is not balanced between intervention and control arms, we will calculate Mantel

Haenszel-adjusted relative risks (RR). For secondary outcomes, we will also assess differences in the proportion of participants.

3. **Calculation of the sample size**. We hope to increase retention in HIV care from 50% to 70% one year after enrollment in the study clinic among HIV+ MSM. With 104 participants in each arm, we will have 80% power to detect this difference.

Our main outcome is the degree of loss to follow-up. Retention in care at the study HIV service (as opposed to being lost to follow-up) is the primary outcome, and retention in any HIV clinic will be a secondary measure. Participants lost to follow-up will be considered as not retained. We will measure the retention in an establishment of the Ministry of Health (MINSA). MINSA provides care to more than 60% of Peruvians (73). Since retaining subjects in our public health system is an important goal, we have not adjusted the sample size calculation based on the potential loss of subjects to follow-up.

OPERATIONALIZATION OF VARIABLES

Table 2. Operationalization of variables.

Variable	Туре	Options	Source				
Age	Continuous	> 18	Online follow-up survey				

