Education	Categorical	Secondary, Technical, Superior,	Online follow-up survey				
Civil status	Categorical	Single, Married, Outgoing, Coupled	Online follow-up survey				
Employment situation Categorical		Unemployed, Employed	Online follow-up survey				
Nationality	Categorical	Peruvian, Foreign	Online follow-up survey				
sexual orientation	Categorical	Gay, Bisexual, Straight	Online follow-up survey				
Diagnosis date	Date	Day month Year	Clinic history; dating record				
Treatment start date	Date	Day month Year	Clinic history; dating record				
Attended appointment dates	Date	Day month Year	Clinic history; dating record				
Viral load	Continuous		Clinic history				
CD4	Continuous		Clinic history				
alcohol use	numeric		Online follow-up survey				
Condom use, last encounter	Categorical	Yes, No	Online follow-up survey				
Email	Text		enrollment sheet				
Cell phone number	Numeric	NA	enrollment sheet				
Arm	Categorical	Control, Intervention	Study Database				
Retention in HIV care	Categorical	If not; Attend three appointments for HIV care that are 90 days or more apart within a one-year period (at the study HIV center)	Clinic history; dating record; online follow-up survey; WelTel system				

TIMELINE

Actividades		Year 1			Year 2			Year 3			Year 4					
	1	2	3	4	1	2	3	4	1	2	3	4	1	2	3	4
Recruitment/Enrollment																
Delivery of intervention																
Monitoring and analysis																
Manuscript development																

REFERENCES

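### The valid, adequately powered primary comparison makes no planned use of attendance before enrolment; one pre-specified adjustment factor would be a cheap and modest gain in precision

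*Combined protocol and SAP*

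**What the plan says.** Under Analysis plan, Statistical analysis, the main outcome is compared as the proportions who "were retained in care in both groups, as a cumulative incidence rate". Adjustment is conditional: it applies when any variable of "interest is not balanced between intervention and control arms, we will calculate Mantel"-Haenszel relative risks. No variable is named and no threshold for imbalance is given.

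Under Enrollment and randomization, men are "randomly divided into intervention or control arm (1:1 ratio) using computer generated random numbers". No strata are stated, and the information taken before allocation does not include attendance history.

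The eligibility criteria ask that a man "has been diagnosed HIV positive" and set no minimum or maximum time in care. Both newly diagnosed and established patients of the service can therefore enter.

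Table 2 lists "Attended appointment dates", taken from the clinic history and appointment record, without a time window. Under Data sources for the main result, retention is verified from enrolment sheets and from "physical medical records from the HIV service, reception appointment notebooks, and with a final follow-up survey". No variable for attendance before enrolment is defined anywhere.

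**The concern.** For a man already in care, visit-keeping in the year before enrolment is the same behaviour as the outcome, recorded in the same place and fixed before allocation. It is a natural candidate for a prognostic covariate. Most other covariates in Table 2 come from the online follow-up survey and may be missing for men who leave care; chart attendance does not depend on a survey response.

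Adjusting for a prognostic factor sharpens the estimate whether or not the arms look balanced. A rule that adjusts only after an imbalance has been seen does not secure that gain, and it makes the choice of estimate depend on the data. At stake is some precision and power that could be had without recruiting more men.

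**Working it through.** **Inputs.** From the documents: 50% vs 70% retained, 104 per arm, 80% power. Assumed, because not stated: two-sided 5% test. Also assumed, because the documents give no figure: the share of outcome variance that prior attendance explains (R²) and the share of men with a usable history.

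**The plan's own figure.** The mean proportion is 0.60. Without continuity correction, n = [1.96√(2×0.6×0.4) + 0.8416√(0.25+0.21)]² / 0.20² = 93 per arm. The continuity-corrected value is (93/4)[1 + √(1 + 4/(93×0.20))]² = 102.8, so 103. The simpler pooled formula gives 94.19, and 103.95 after correction, so 104. The stated size is reproduced. At 104 per arm, power is 80.5% with the correction and, without it, Φ[(0.20 − 1.96√(0.48/104)) / √(0.46/104)] = 84.3%. The 95% CI half-width for the risk difference is 1.96√(0.46/104) = 13.0 points.

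**Gain for a given R².** Adjustment multiplies the variance by (1 − R²), so effective n per arm is 104/(1 − R²).

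| R² | Effective n per arm | Equivalent extra men | Power (uncorrected) |
|---|---|---|---|
| 0 | 104.0 | 0 | 84.3% |
| 0.05 | 109.5 | 11 | 86.1% |
| 0.10 | 115.6 | 23 | 87.9% |
| 0.15 | 122.4 | 37 | 89.6% |
| 0.20 | 130.0 | 52 | 91.3% |

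At R² = 0.10 the CI half-width falls from 13.0 to 12.4 points.

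**What R² needs.** The mean within-arm variance is (0.25 + 0.21)/2 = 0.23. Take a factor that splits men with a history 50/50, a retention gap g between good and poor attenders, and a share f of men with a history. Then R² = f × 0.25 × g² / 0.23. With f = 1, gaps of 20, 30 and 40 points give 0.04, 0.10 and 0.17. With g = 0.40, reducing f to 0.5 or 0.25 gives 0.09 or 0.04. The benefit shrinks in proportion to the share with a history.

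**Simulation of the three-level factor.** Stratified Mantel-Haenszel test; overall 50% vs 70%; common odds ratio; simple randomisation; 40,000 trials per case for the last two rows. Assumption: men without a usable history have 50% control retention.

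| Men with a usable history | Poor/good attenders 30%/70% in control arm | 35%/65% |
|---|---|---|
| All | about 85% to 90% | about 85% to 87% |
| Half | 85.2% to 86.8% | 85.0% to 85.5% |
| A quarter | 84.6% to 85.2% | 85.0% to 84.7% |

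These gains are smaller than the R² formula suggests. A common odds ratio narrows the gap between strata in the intervention arm, and stratifying has a small cost of its own. In a separate simulation, a two-level factor with no predictive value lowered power from 84.6% to 83.9%, and the type I error of the adjusted test was 4.8%.

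**Classification check.** Three visits at least 90 days apart need at least 2 × 90 = 180 days in care. A man enrolled four months after entry cannot have met the rule, however well he attended. Grouping him with poor attenders would blunt the factor.

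**The case against.** The strongest reply is that nothing here is wrong. An unadjusted comparison of proportions in a 1:1 randomised trial is valid, and the planned size meets its stated power without adjustment. That stands.

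A reader might infer that every man has an attendance history in the chart. The documents do not support this: a man new to the service can enrol, and the standard care arm is described largely as the pathway after a new diagnosis. The share already in care is not given, and if most men are new there is essentially no gain.

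A reader might also infer that the plan rules out using prior attendance. It does not. Appointment dates are listed without a time window, and the Mantel-Haenszel clause could take in prior attendance, but only after an observed imbalance. That leaves the gain to chance.

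Nor is the randomisation shown to be at fault. Stratifying it would need a chart check before allocation, a step the enrolment procedure does not describe. Adjustment in the analysis needs no such step.

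Finally, the work is not free. The sources are physical records and notebooks, so an extra year of visit dates must be abstracted by hand, and unblinded providers should not be the ones to do it.

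**Conclusion.** The point holds as a low-cost improvement. The plan makes no commitment to use attendance before enrolment, and its conditional rule does not supply one. The likely gain is about 2 to 5 points of power if all men have a usable history, about 1 to 2 if half do, and about zero if a quarter do, against about 85% unadjusted. The loss is under 1 point if the factor predicts nothing. These figures rest on assumed predictive strengths (35%/65% and 30%/70% control retention), on 50% control retention in men without a history, and on a two-sided 5% test.

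It would go too far to say that the trial is underpowered or that its primary result would be biased. The stated power is reproduced, and the unadjusted estimate is valid.

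**What to change.** Change the analysis only; leave the randomisation as it is. Pre-specify, before any outcome data are seen by arm, that the primary estimate is a Mantel-Haenszel relative risk of retention in all 208 men, stratified on one baseline factor whatever the observed balance. Report the unadjusted proportions and relative risk beside it. The levels are:

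1. new to the service, or in care for too short a time before enrolment to have met the three-visit rule (under 180 days);
2. in care long enough, and met the rule in the 12 months before enrolment;
3. in care long enough, and did not meet it.

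Abstract the visits only from records dated before enrolment, by someone blind to arm. Report how many men fall in each level, since that decides how much the adjustment can help.

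The cost is one paragraph in the analysis plan and hand abstraction of one earlier year of visit dates from charts already in use. No extra participants or study visits are needed.

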- 4. Standard care arm. In 2018, the government published new national guidelines for HIV care (65). After pre-test counseling, the diagnosis of HIV is made with two rapid tests. Those who test positive for both tests receive post-test counselling, including emotional support, and are linked to an ART initiation center, ideally within the same week. During the first medical appointment after diagnosis, laboratory tests including CD4 and viral load (VL) are requested. In most cases, initiation of antiretroviral treatment (ART) occurs at the second medical appointment when basic laboratory results are available. Currently, it is not mandatory to have CD4/CV results available to start ART. ART, viral load and CD4

lab tests are provided free of charge. It is recommended that patients have CD4 counts and viral load testing twice during the first year. A one-month supply of ART is initially provided. If patients are adherent, nurses dispense ART every 3 months and also assess adherence.

Table 1. Summary of the study: exposures, results and design.

Component	Sub-	Description						
	component							
	Basic follow-up	Weekly automatic SMS with the question "How are you?" or similar						
	SMS (check-in)	messages. This will be shipped for 6 months.						
Intervention	Calls	The provider can call participants who have a problem.						
arm	Appointment	SMS reminder one week before each appointment for HIV care.						
(exposure)	reminders							
	Primary	Retention in HIV care up to 1 year after enrollment, defined as attending 3						
Results		appointments that are 90 days apart within a 1-year period.						
	Desing	Randomized controlled trial with a parallel group.						
		We aim to increase retention in HIV care from 50% to 70%. With 104						
	Sample size	participants in each arm, we will have 80% power to detect this difference						
Design	Follow-up	6 months (intervention); 12 months (retention measure).						
	Theory	The behavior change wheel framework and its model of Capability,						
		Opportunity, Motivation and Behavior.						
	Standard of care	Post-test counselling, including emotional support and linkage to ART						
Control arm		initiation, ideally within a week. ART, CD4, and viral load laboratory tests are						
		provided free of charge in Peru.						

Analysis plan:

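### The conditional Mantel-Haenszel adjustment may draw on final-survey values that can select on retention; name the crude all-randomised estimate as primary and limit covariates to pre-randomisation data

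*Combined protocol and SAP*

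**What the plan says.** The statistical analysis item of the Analysis plan starts with an unconditional comparison by arm: "for the main outcome, we will compare the proportion of MSM who" stayed in care. A conditional step follows, in a sentence containing "interest is not balanced between intervention and control arms, we will calculate Mantel" and ending in Haenszel-adjusted relative risks, in the plural. The item gives no list of variables, no balance criterion, no rule for missing covariates and no statement of which estimate is primary.

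The sample-size item adds: "Participants lost to follow-up will be considered as not retained".

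Table 2 (Operationalization of variables) names "Online follow-up survey" as the only source for eight variables: age, education, civil status, employment, nationality, sexual orientation, alcohol use and condom use. The data-sources item describes one survey, at the end: "The data from the final follow-up online survey completed by the participants". Viral load and CD4 come from the clinic history with no time point, while the description of standard care says "It is recommended that patients have CD4 counts and viral load testing twice during the first year".

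Before randomisation, the enrolment section lists a cell phone number and "brief general information (first name, date of diagnosis, email". Age must be known well enough to check eligibility ("18 years or older; 3) has been diagnosed HIV positive"), but Table 2 does not source it from enrolment.

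**The concern.** The usual candidates for a balance check are demographic, and in this plan they have no listed source before randomisation. A man with no final survey has no value for them. An adjusted RR must then either drop him or place him in a stratum for unknown, and membership of that stratum may itself depend on retention. Either route undercuts the rule that a man lost to follow-up counts as not retained, because such men are plausibly the least likely to answer a final survey. The balance check would also run on responders only.

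For fixed traits such as age, the problem is non-response alone. Alcohol use, condom use, employment, viral load and CD4 may also change after randomisation, so adjusting for late values could remove or distort part of the effect.

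At stake is whether an adjusted RR still describes all 208 randomised men. Response could differ by arm, since only one arm receives six months of messages.

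**Working it through.** **Inputs.** Retention 50% v 70% and 104 men per arm are from the sample-size item. The documents do not state alpha; two-sided 5% is assumed. They give no survey response rates, so those below are assumptions shown over a range.

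**The plan's own figure.** Without continuity correction, n = [1.96√(2×0.6×0.4) + 0.8416√(0.5×0.5 + 0.7×0.3)]² / 0.20² = (1.3579 + 0.5708)² / 0.04 = 93 per arm. With correction, (93/4)[1 + √(1 + 4/(93×0.20))]² = 102.8, so 103. The stated 104 is reproduced to within one man. Power at 104 per arm is 84% uncorrected and 81% corrected.

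**Responders only.** Let p be retention, r response in retained men and s response in non-retained men. Retention among responders is q = pr / [pr + (1−p)s]. With r = 0.90 and the same s in both arms:

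| s | q control | q intervention | RR | Men left | Power | With unknown stratum: RR, power |
|---|---|---|---|---|---|---|
| 90% | 0.45/0.90 = 0.500 | 0.63/0.90 = 0.700 | 1.40 | 187 | 79% | 1.40, 84% |
| 70% | 0.45/0.80 = 0.563 | 0.63/0.84 = 0.750 | 1.33 | 171 | 73% | 1.37, 81% |
| 50% | 0.45/0.70 = 0.643 | 0.63/0.78 = 0.808 | 1.26 | 154 | 61% | 1.31, 74% |
| 30% | 0.45/0.60 = 0.750 | 0.63/0.72 = 0.875 | 1.17 | 137 | 44% | 1.23, 62% |

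Men left is 104 times the sum of the two denominators, for example 104 × (0.70 + 0.78) = 153.9. RR for responders is exact. Power, and the unknown-stratum figures, are simulated (Mantel-Haenszel RR, Greenland-Robins variance, 104 per arm, one non-prognostic binary covariate split 50:50, 200,000 trials per scenario). The crude RR in all 208 men is 1.40 with 84% power.

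**Opposite direction.** If retained men respond less (50%, against 90% in non-retained men, both arms), q is 0.25/0.70 = 0.357 and 0.35/0.62 = 0.565. The responder RR is 1.58, away from 1.

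**Response differing by arm, true effect present** (r = 90%; s given as control/intervention):
- 70/50: 0.808/0.5625 = 1.44.
- 50/70: 0.750/0.643 = 1.17, power 29%.
- 60/40: 0.840/0.600 = 1.40, no shift.

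**No true effect** (50% retention in both arms, r = 90%, responders only). At 40/60, for example, q is 0.45/0.65 = 0.692 and 0.45/0.75 = 0.600, an RR of 0.87 where the truth is 1. Simulated type I error:
- equal response, 50/50: 4.7%;
- 10-point arm difference, 50/60 and 50/40: 8% and 9%;
- 20-point arm difference: 13% (90/70), 17% (70/50 and 50/70), 21% (40/60 and 60/40), 27% (30/50);
- crude RR in all men: 4.4%.

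An unknown stratum lowers the 17-21% cases to 9-12% but does not remove the error.

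**Adjustment only when triggered.** The figures above adjust in every trial and treat the adjusted test as decisive. Suppose instead that imbalance means p<0.05 on any of eight independent survey variables. Chance alone then triggers adjustment in 1 − 0.95⁸ = 34% of trials. If the adjusted RR (responders only, first unbalanced variable) replaces the crude RR only in those trials, simulated results with 100,000 trials are:
- power 75% at 50/50, 70% at 30/30 and 65% at 50/70;
- type I error 9.9% at 40/60, 8.7% at 50/70 and 5.7% at 50/60.

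With one candidate variable, type I error in those three null cases is 4.5-5.3%, and power in the three effect cases is 81-82%.

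**The case against.** The strongest reply is that the crude comparison is stated without condition, and the loss-to-follow-up rule implies that it covers all 208 men. On that reading the adjusted RR is an extra, and the primary test is untouched. This largely stands: the crude comparison naturally leads. What remains is that the plan does not say so, and nothing prevents an adjusted RR from leading the report of a trial in which providers and participants are unblinded.

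A second reply is that baseline variables were meant. Table 2 is a general data dictionary and does not mark candidates for adjustment, so the plan does not commit to using survey variables. But it does not bar them, and its own table gives no pre-randomisation source for those eight.

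A reader might infer that the undefined trigger is itself the main harm. The figures do not support that. With true baseline variables and a mechanical p<0.05 trigger, simulated type I error is 4.8%. Free choice of the most favourable among the crude RR and eight single-variable adjusted RRs gives 5.9% to 7.8%. The larger distortion comes from the survey as the source.

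A reader might also infer that adjustment always pulls the effect towards 1. In responders that holds only when retained men respond more, equally in both arms; the 1.58 case shows the reverse.

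**Conclusion.** The plan leaves open an adjusted analysis that can discard, or set apart by outcome, the men it elsewhere counts as not retained. This should be corrected.

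The size is conditional. If adjustment is made, taken as decisive, and 90% of retained men respond, equal non-retained response of 70/50/30% gives RR 1.33/1.26/1.17 and power 73/61/44%, against 1.40 and 84% for the crude RR. Type I error of about 13-27% needs a 20-point arm difference in non-retained response and covers only the cases checked. Under the assumed 34% trigger the effect shrinks to, for example, 75% power at 50/50 and about 10% type I error at 40/60. If response is unrelated to retention there is no bias, only fewer men.

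The stronger reading, that the trial's primary result is biased as planned, is not supported: the documents do not say that the adjusted RR will replace the crude comparison or that survey variables will be used, and they give no response rates.

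**What to change.** Replace the conditional sentence with text to this effect: *The primary estimate is the crude relative risk (95% CI), with the risk difference, in all randomised men, with loss to follow-up counted as not retained. Any Mantel-Haenszel relative risk is supportive, includes all randomised men, and uses only variables recorded or fixed before randomisation and named before data are seen. Final-survey values and post-randomisation laboratory values are not used for adjustment.*

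Time since diagnosis is one usable variable, because the date is already taken at enrolment; Table 2 should then list the enrolment sheet as a source for it. The documents do not show that it is prognostic, so it is an example only. Fixed traits such as age, education and nationality may be used if they are recorded on the enrolment sheet.

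The cost is one or two SAP sentences and, optionally, a few enrolment-sheet fields. The sample size does not change.

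### Eight possible adjustment variables are sourced only from what appears to be the end-of-study survey, so a triggered Mantel-Haenszel RR may rest on responders and be biased in either direction

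*Combined protocol and SAP*

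**What the plan says.** **Source of the covariates.** In Operationalization of variables, Table 2, the Source entry for eight rows is "Online follow-up survey" and nothing else: age, education, civil status, employment situation, nationality, sexual orientation, alcohol use and condom use at last encounter.

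**Timing of the survey.** Data sources for the main result, in the Analysis plan, describes one survey: "The data from the final follow-up online survey completed by the participants will be exported to the physical database". It also lists that survey among the means of verifying retention: "reception appointment notebooks, and with a final follow-up survey".

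**What is taken before randomisation.** Enrollment and randomization, item 2 of Procedures, says: "Participants will be randomly assigned after providing their cell phone number and brief general information (first name, date of diagnosis, email"). It adds: "Arm assignments will be in sequentially numbered sealed envelopes". Table 2 names the enrolment sheet as source only for email and cell phone number.

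**Trigger for adjustment.** Under Statistic analysis, if any variable of "interest is not balanced between intervention and control arms, we will calculate Mantel"-Haenszel-adjusted relative risks. The variables are not named and no threshold for imbalance is given.

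**Missing data.** The one rule concerns the outcome: "Participants lost to follow-up will be considered as not retained". Nothing is said about a missing covariate.

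**The concern.** A balance check and a covariate adjustment should use values fixed before treatment starts and known for everyone randomised. Taken as written, Table 2 offers neither for these eight variables.

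First, only men who complete the survey would have values. The outcome is staying in care at the clinic, so men who drop out of care are plausibly less likely to complete a final survey. Response may also differ by arm, because only the intervention arm has six months of weekly two-way messages. A complete-case adjusted RR then conditions on something related to the outcome and possibly to the arm.

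Second, alcohol use, condom use, employment and civil status can change after randomisation. Measured at the end, they do not describe balance at enrolment even if every man answers.

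The adjusted RR could then disagree with the crude one because of who answered, while being presented as the version corrected for imbalance.

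**Working it through.** **Inputs from the documents.** Retention 50% control and 70% intervention, so the true RR is 0.70/0.50 = 1.40; 104 men per arm; 1:1 allocation. The stated sample size reproduces closely: the two-proportion formula at two-sided 5% (assumed; alpha is not stated), 80% power and continuity correction gives 103 per arm against the stated 104.

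**Inputs that are assumed.** The documents give no survey response rates. Let r1 be the response rate in retained men (90% in both arms) and r0 the rate in non-retained men (varied).

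**Formula.** In an arm with true retention p:

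- overall response = p·r1 + (1−p)·r0
- retention among responders = p·r1 / [p·r1 + (1−p)·r0]

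When r1 is the same in both arms, dividing the two responder proportions gives

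responder RR = true RR × (overall control response ÷ overall intervention response).

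Example with r0 = 60% in both arms:

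- control: 0.45/(0.45 + 0.30) = 60.0%, response 75%
- intervention: 0.63/(0.63 + 0.18) = 77.8%, response 81%
- RR = 1.40 × 0.75/0.81 = 1.30
- men analysed = 104 × 0.75 + 104 × 0.81 = 78.0 + 84.2, about 162

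**Results**

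| True retention (control / intervention) | r0 control / intervention | Responder retention | Overall response | Responder RR |
|---|---|---|---|---|
| 50% / 70% | 90% / 90% | 50.0% / 70.0% | 90% / 90% | 1.40 |
| 50% / 70% | 60% / 60% | 60.0% / 77.8% | 75% / 81% | 1.30 |
| 50% / 70% | 40% / 40% | 69.2% / 84.0% | 65% / 75% | 1.21 |
| 50% / 70% | 20% / 20% | 81.8% / 91.3% | 55% / 69% | 1.12 |
| 50% / 70% | 60% / 40% | 60.0% / 84.0% | 75% / 75% | 1.40 |
| 50% / 70% | 60% / 30% | 60.0% / 87.5% | 75% / 72% | 1.46 |
| 50% / 70% | 40% / 60% | 69.2% / 77.8% | 65% / 81% | 1.12 |
| 50% / 50% | 40% / 40% | 69.2% / 69.2% | 65% / 65% | 1.00 |
| 50% / 50% | 40% / 60% | 69.2% / 60.0% | 65% / 75% | 0.87 |
| 50% / 50% | 40% / 30% | 69.2% / 75.0% | 65% / 60% | 1.08 |

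In the equal-response rows with r0 of 60%, 40% and 20%, about 162, 146 and 129 of the 208 men are analysed. With r1 = 80% instead of 90%, those RRs are 1.32, 1.24 and 1.13.

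**Does stratifying remove it?** The plan would report a Mantel-Haenszel RR, so I repeated the calculation on expected counts with an unbalanced binary covariate: prevalence 50% control and 35% intervention, control retention 40% with it and 60% without, and RR 1.40 in each stratum. This set-up departs from the planning values. Intervention retention is 0.35 × 0.56 + 0.65 × 0.84 = 74.2%, and the full-data crude RR is 0.742/0.50 = 1.48. The correct adjusted value is 1.40, which is recovered when response does not depend on retention. Among responders, the Mantel-Haenszel RR is 1.29, 1.21 and 1.11 for equal r0 of 60%, 40% and 20%; 1.38 for 60%/40%; and 1.43 for 60%/30%. With no true effect it is 0.88 for 40%/60% and 1.08 for 40%/30%. Stratifying does not remove the bias.

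**The case against.** The strongest objection is that Table 2's Source column is weak evidence of what is collected when. It says online follow-up survey, not final survey; the link comes from reading it with the Analysis plan. The column is also demonstrably loose. Date of diagnosis is taken at enrolment, yet Table 2 lists only clinic sources for it. The retention row reads "Clinic history; dating record; online follow-up survey; WelTel system", which leaves out the enrolment sheets that the Analysis plan names and adds the WelTel system, which it does not. Age must be known to apply the eligibility criterion of 18 years or older. The enrolment list may be only a summary. This stands as a limit: the items may in fact be recorded at enrolment, in which case correcting the Source column settles the collection question. But no other survey is described, and someone following the plan as written would use the final one.

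It is also fair to say that no text calls these eight the variables of interest, and that the trigger could instead be applied to diagnosis date, CD4 or viral load. Four things must coincide for the response bias: one of the eight is chosen, it is unbalanced, the analysis is complete-case, and response depends on retention. That limits severity. It does not make the route remote, because every demographic variable in Table 2 is survey-only, and an ordinary balance table draws on those.

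Finally, every response rate above is assumed. The figures show what could happen, not what is likely.

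**Conclusion.** The concern holds, as a conditional one. Following the plan as written can make the balance check and the adjusted RR depend on end-of-study responders, and on values that may have changed after randomisation.

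Direction depends on the response pattern. If non-retained men answer less often, equally in both arms, the RR is pulled toward 1 and no false effect arises under the null. If their response differs by arm, the RR can be too small, unbiased or too large, and can depart from 1 when there is no effect. At the rates assumed, a shift of 0.1 to 0.3 from a true RR of 1.40 is possible.

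The crude comparison of all 208 men is not affected through this covariate route. The survey's separate role as a source for retention itself is not assessed here. Because only a conditional adjusted analysis is exposed, this is minor to moderate: it should be fixed, but it does not undermine the main comparison.

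**What to change.** 1. Name the adjustment variables before any outcome by arm is seen.
2. Record any chosen from these eight on the enrolment sheet before the envelope is opened, and change their Table 2 source to the enrolment sheet. If they are already recorded there, correct Table 2 to say so.
3. Add to the analysis plan:
   > Only variables recorded at or before enrolment, or fixed ones such as age that are back-calculated to enrolment and obtained for all men regardless of survey response, enter the balance table and the adjusted RR. A man with no value recorded at enrolment stays in the adjusted analysis in a missing-value stratum. The crude comparison of all randomised men remains primary.
4. If enrolment is closed, adjust only for age from eligibility or clinic records, date of diagnosis, and chart values dated on or before enrolment where available. Do not adjust for values known only from survey responders.

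**Cost.** A few more enrolment questions, with the change to the enrolment form (and possibly a protocol amendment) that this implies, an edit to Table 2, and three sentences in the analysis plan. If enrolment is closed, the cost is fewer adjustment variables.
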